# List of abbreviations

(Abbreviations are listed alphabetically)

AE:	Adverse event
AR:	Adverse reaction
BCVA:	Best-corrected visual acuity
ETDRS:	Early Treatment Diabetic Retinopathy study chart
CRF:	Case Report Form
ICH-GCP:	International Conference on Harmonization - Good Clinical Practice
IOP:	Intraocular pressure
logMAR:	Logarithm to the minimal angle of resolution
OCT:	Optical coherence tomography
SAE:	Serious adverse event
SAR:	Serious adverse reaction
UAR:	Unexpected adverse reaction
SUSAR:	Suspected unexpected serious adverse reaction

#### Purpose

Myopia (nearsightedness) is increasing in prevalence throughout the world. It is associated with a risk of potentially blinding complications such as retinal detachment and myopic maculopathy. There is a direct association between the degree of myopia and the risk of complications. Myopia develops in childhood and during adolescence. To prevent higher degrees of myopia, we need to halt disease progression in children and teenagers. Low-dose atropine eye drops have been shown to reduce myopia progression by 50% in Asian populations but its effect in non-Asian populations is unknown. The aim of this study is to investigate if low-dose atropine can reduce myopia progression in Danish children and teenagers. The study is an investigator initiated randomized clinical trial conducted as a collaboration between three Danish Eye Departments covering all of Denmark.

#### Introduction

Globally, myopia is a common cause of visual loss. (1,2) Myopia is the most common cause of moderate and severe visual impairment, (3,4) the second most common cause of blindness. (3,4) The prevalence of myopia is increasing. (1,2,5,6) In East Asia 80-90% of school-leavers are myopic (7) whereas Europeans are less affected, however still approximately 20% of 12-13 years children (8) and 47% of young adults (25-29 years) are myopic. (6) Myopia and especially high myopia (-6 diopters or more) increases the risk of sightthreatening eye diseases such as glaucoma, cataract, retinal detachment and myopic maculopathy. (9-11) Accordingly, myopia is now an immediate priority of the World Health Organization's Global Initiative for the Elimination of Avoidable Blindness, and potential interventions to reduce myopia progression are warranted. (12)

Humans are born hypermetropic (farsighted) and during childhood the eye grows to reach adult size in a process termed emmetropization. In some children, eye growth and especially axial length elongation exceeds the normal growth rate and progress beyond normal adult length resulting in myopia. (13) In economically developed societies, most myopia appears during childhood (8-12 years), particularly during the school years. Since myopia typically develops during childhood it is relevant and necessary to investigate possible methods of halting the progression in children.

Myopia is the result of excessive elongation of the eyeball with light focusing in front of the retina causing a blurred image. It has yet to be established why this elongation develops but a number of theories have been proposed. Most researchers agree that both environmental and genetic factors contribute to the Version: 5

development of myopia. (9,14) A small proportion of myopia is familial, generally early in onset and of high level (-6 diopters or more). The chromosomal locations characterized so far for high familial myopia do not seem to be relevant to school myopia. (15) Studies suggest that genetics are only accountable for a small proportion of myopia cases whereas the increasing prevalence is predominately the result of environmental factors. (9,15,16) Still, the exact environmental factors and the relative contribution of each factor remain elusive. Two major risk factors identified are intensive education, possibly by a link to near work stress, and limited time spent outdoors. (17) Near work is one of the most frequently cited risk factors for myopia. Near work causes convergence of the eyes and accommodation – both have been used to explain the progression of myopia (use-abuse theory) although an association has not been consistently observed. (17-19) In animal models, axial length and choroidal thickness may be controlled by retinal defocus. (18-20) Changes in the peripheral defocus by special contact lenses in human studies induces a prompt increase in choroidal thickness. (21) In the myopic human eye, the relative peripheral hyperopia is induced by the oval shaped eyeball, which may signal to further axial growth and progression of myopia possibly through signal pathways in the choroid. (22,23) In other words, in addition to genetic predisposition and near work a mismatch between image focusing in the central and peripheral retina have received theoretical and experimental support as likely causes for myopia development and progression. Thus, myopia is of diverse etiology.

Many studies have investigated possible preventive treatments of myopia. Time spent outdoors may reduce the odds of myopia onset by 2% per additional hour spent outside per week. (22) Orthokeratology contact lenses, which are rigid gas permeable contact lenses reshaping the corneal surface when worn nightly, have been shown to reduce axial elongation by 36-46%, (23-27) but may be associated with infectious keratitis. (28) In terms of relative peripheral hyperopia, the evidence is contradictory. Previous studies have shown that the peripheral defocus only have little influence on the risk of myopia onset, myopia progression and axial elongation. (29) Correspondingly, treatment strategies with novel spectacle lenses aimed at reducing the peripheral hyperopic defocus showed no statistically significant difference in the rates of myopia progression between the control and novel spectacle lens wearing eyes. (30) However, recent studies show that soft multifocal contact lenses slow myopia progression by a weighted average percent of 36.4% and axial elongation by a weighted average percent of 37.9%. (31)

Atropine, a non-selective muscarine acetylcholine receptor antagonist and pirenzepine, a selective muscarine (M1) receptor antagonist, reduces myopia progression by approximately 50% in Asian children. (32,33) The effect of pirenzepine was shown in 2 randomized clinical trials but the use of pirenzepine was

associated with side effects such as papillary conjunctivitis, photophobia and difficulties with near work. (34,35) Atropine has been shown in several animal (18,36,37) and human studies (38,39) to prevent axial elongation. However, the underlying basic mechanism for this effect in still unclear.

The effect of atropine is dose dependent with high dose (1%) superior (≥0.50 diopter reduction in myopia/year) to other treatments. (33) However, the side effects of high dose treatment including photophobia related to pupil dilation, reading problems and headache together with the profound myopic rebound effect after treatment cessation make treatment unacceptable for standard care. (40) The Atropine for Treatment of Childhood Myopia (ATOM 2) study (41) compared the safety and efficacy of 3 lower doses of atropine (0.5%, 0.1% and 0.01%). The study was a 60-month doubled masked, randomized, controlled trial including 400 Asian children aged 6-12 years. A washout period of 12 months was included, and surprisingly atropine 0.01% was found superior in reducing myopia progression (-1.4 diopters less) compared to 0.5% and 0.1% after 60-months mainly because of less rebound effect in myopia progression when treatment was stopped. The side effects of atropine 0.01% and 0.1% were low. Pupil size under both photopic and mesopic conditions were only 1 and 3 millimeters, respectively, and accommodation amplitude decreased to 11.3 diopters and 3.8 diopters, respectively. Allergic conjunctivitis was seen in 4.5% of the children in the 0.1% group but in no children in the 0.01% group. (41)

Atropine appears to have the strongest clinical effect on reducing myopia progression of all reported modalities so far, and low-dose treatment seems favorable due to limited side effects and greater longterm effects because of the rebound catch-up myopia seen after treatment cessation with higher doses. However, these results are based on Asian studies, and it is unknown whether similar results can be replicated in Danish children, since environmental factors, heritability and genetics may influence the effect of the treatment.

## Hypothesis

The main hypotheses tested in this study are:

- 0.01% atropine one drop nightly reduces the progression of childhood myopia in Danish children.
- 0.01% atropine one drop nightly is safe and with no significant side effects.
- A 6-month loading dose of 0.1% atropine followed by a 0.01% atropine maintenance dose is superior to single 0.01% atropine.
- 0.1% atropine one drop nightly is safe and has tolerable side effects.

- The rebound effect after stopping both atropine regimens is limited.
- Choroidal thickness is a predictor for the progression of childhood myopia.

## Methods

#### Study design

The study is designed as a randomized, double-masked, multicenter, 36-month prospective, phase II 1:1:1 study of safety and efficacy of 0.1% atropine loading dose to single 0.01% atropine versus placebo. In phase 1 (treatment phase), the participants will be randomized in a 1:1:1 ratio to receive 0.1% atropine loading dose for 6 months followed by 0.01 % atropine for 18 months (n=50) versus 0.01% atropine (n=50) or placebo (n=50) for 24 months. The atropine is administered as one eye drop daily in each eye at bedtime. In phase 2 (washout phase), treatment will be stopped and the participants monitored for 12 months. A schematic presentation of the 3 interventional groups are shown in Figure 1.

Figure 1: A schematic presentation of the 3 interventional groups.

## Study period

The inclusion period began on January 1, 2019 and was completed at the end of April 2021. 124 potential candidates were screened, and 97 research participants were randomized for the intervention. Patients will receive 24 months treatment with atropine or placebo followed by a 12 months washout phase to allow for detection of a possible rebound effect. The last patient visit is scheduled to take place on April 30, 2024. Statistical evaluation of the study results and reporting of findings is scheduled to take approximately 8 months with an expected completion of the study on December 31, 2024. A rough time schedule is presented in Table 1. The authorities will be informed when the study has finished. If finished at the

	2018				2019				2020					20	21		2022				2023				2024			
Quarter	1	2	3	4	1	2	3	4	1	2	3	4	1	2	3	4	1	2	3	4	1	2	3	4	1	2	3	4
Application for Danish Medicines Agency	•	•																										
Application for National Committee on Health Research Ethics			•	•																								
Application for Data Protection Agency			•	•																								
Recruitment and follow-up					•	•	•	•	•	•	•	•	•	•	•	•	•	•	•	•	•	•	•	•	•	•		
Ph.D. courses					•	•	•	•	•	•	•	•	•	•	•	•			•	•	•	•	•	•	•	•		
Papers and theses																•	•	•	•	•	•	•	•	•	•	•	•	•

planned date authorities will be informed within 90 days, if finished earlier authorities will be informed within 15 days.

#### Table 1: Time schedule

#### Facilities

Clinical research facilities have been established at (1) Department of Ophthalmology, Rigshospitalet, (2) Department of Ophthalmology, Aarhus University Hospital and (3) Department of Ophthalmology, Vejle Hospital. All necessary equipment for the study as well as office facilities are already available at the facilities. All three institutions are well-trained in performing GCP clinical trials.

#### Randomization

Participants will be randomly assigned using a computer algorithm to 1 of the 3 interventional groups if the patient and his/her parents consent to participation in the study after the screening visit and after having received oral and written information on the study. Written informed consent will be obtained from parents and verbal assent will be obtained from children before randomization. Randomization will be done in 3 strata defined by research facility (i.e. (1) Department of Ophthalmology, Rigshospitalet, (2) Department of Ophthalmology, Aarhus University Hospital and (3) Department of Ophthalmology, Vejle Hospital). Randomization will be performed using a computer algorithm which is in-built in the electronic clinical report form (eCRF). The algorithm is based on a list of randomly created numbers that are each assigned to a specific treatment. The randomization list is stored by the sponsor-investigator so that each

randomization number is listed on a sealed envelope containing the specific treatment for that randomization number. All envelopes are stored together and in manner that is not accessible to other study investigators. In case of an emergency, the sealed envelope for the randomization code concerning a specific participant may be opened by the sponsor-investigator whereby sponsor-investigator will be unmasked to treatment status. If the code is broken, the sponsor-investigator will no longer take part in any of the directly participant related examinations, and the sponsor-investigator will not share this information with any other study investigators.

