#### Blinding

Allocation concealment is performed by masking the investigators, additional study team performing the ocular measurements, parents and patients to randomization status throughout the entire study period. All statistical analyses will be performed masked to randomization status. A list linking participant study identification number to randomization status will be kept under lock in a designated space unavailable to study investigators. Trial medication will be prepackaged from external collaborator #1 so that bottles are pre-labeled according to the European rules on labelling of trial medicines (see *Appendix 1*) and of similar appearance.

If necessary, sponsor-investigator will be unblinded as to participants treatment status as described above. All statistical analyses will be performed in a masked fashion allowing sponsor-investigator to part of the analyses.

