## Registration of adverse events

At all trial visits, patients are checked for adverse events to the investigational medicinal product. All visits include measuring distant BCVA, IOP, pupil size and accommodation. The patients and parents will also be asked for subjective complaints and symptoms related to the investigational medicinal product. The number of trial visits is illustrated in Figure 2. Patient and parents will be instructed to contact the investigators immediately if vision gets worse, the eye or eye surroundings turns red and/or painful or they become sensitive to light, or experience halos around light sources. If the patient experiences an adverse event or reaction within the trial period, the patient will be monitored and/or treated for as long as it is relevant given the circumstances. Principle investigators will make the decision.

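### As written, the result of an emergency code break may not be passed to the study investigator managing the child, unless that person is the sponsor-investigator

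*Combined protocol and SAP*

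**What the plan says.** The Randomization section (under Methods) sets up a sealed envelope per randomization number for use in an emergency. The envelope "may be opened by the sponsor-investigator whereby sponsor-investigator will be unmasked to treatment status". On storage: "All envelopes are stored together and in manner that is not accessible to other study investigators". On what follows a code break: "the sponsor-investigator will not share this information with any other study investigators".

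The Blinding section adds a second safeguard: "A list linking participant study identification number to randomization status will be kept under lock in a designated space unavailable to study investigators". Its own sentence on unblinding is "If necessary, sponsor-investigator will be unblinded as to participants treatment status as described above", which points back to the Randomization section and names nobody else.

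Responsibility for adverse events is placed elsewhere. Registration of adverse events says that an affected child is monitored or treated for as long as is relevant, and continues: "Principle investigators will make the decision". Criteria for aborting the study has adverse effects of the trial medication treated by standard procedures at the research facilities. Dissemination of findings describes three principal investigators on a steering committee that represents all three departments, and Informed consent speaks of a local principal investigator.

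**The concern.** An emergency code break exists so that someone managing a child can learn the allocation when it is needed. By including one, the protocol accepts that this may happen. The rules around it are written to protect masking and contain no exception for the person handling the emergency. If the rules are followed to the letter, the code can be opened and the result still withheld from the investigator whom the protocol makes responsible.

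The documents show that the arms are not interchangeable for side effects. For the first 6 months one arm receives 0.1% and another 0.01%, a tenfold difference (0.1 / 0.01 = 10), against placebo in the third. Risks, side effects and inconveniences reports, from the cited dose-comparison trial, that the allergic conjunctivitis and dermatitis all arose in the 0.1% group, and that accommodation amplitude fell to 3.8 diopters with 0.1% and 11.3 diopters with 0.01%. The same section lists rare systemic anticholinergic effects of the 1% product. At stake are participant safety and a site's ability to follow its own protocol in an emergency.

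**Working it through.** No figure in the plan bears on this point, so the check is to set the rules side by side and follow the information.

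1. **Who can open an envelope.** The sponsor-investigator is the one person named. No deputy or site-level code break appears. Exclusivity is an inference from this and from the storage rule; the text does not state it in so many words.
2. **Who could find out another way.** The envelopes and the linking list are both closed to study investigators. The electronic case report form runs the randomization algorithm, but no right to unmask a single participant in it is described.
3. **How long masking lasts.** The Blinding section masks the investigators, the measuring team, "parents and patients to randomization status throughout the entire study period". No emergency exception is attached.
4. **Who may be told.** Every study investigator other than the sponsor-investigator is excluded.
5. **Which way information flows.** Under Reporting adverse effects to the authorities, serious events go by email to the sponsor-investigator within 24 hours. Nothing describes an answer going back to the site.
6. **What happens to the person who knows.** After a code break, "the sponsor-investigator will no longer take part in any of the directly participant related examinations". That sentence is not limited to the child concerned.

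The outcome depends on who is responsible for the child:

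| Person responsible | Can that person learn the allocation under the text? |
|---|---|
| Sponsor-investigator | Yes, but must then withdraw from examinations, and may not tell a fellow investigator who takes over |
| Any other study investigator, including another principal investigator | No |
| Clinician outside the study | Not expressly barred, but no route is described |

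The middle row is the conflict. It describes the people to whom the adverse-event sections give the decision and the treatment setting.

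**What an amendment could still reach.** Study period says that inclusion ran from January 2019 to the end of April 2021. A child enrolled at the start would finish treatment in January 2021 (January 2019 + 24 months), before recruitment closed. The last child enrolled would finish treatment around April 2023 (April 2021 + 24 months) and the washout around April 2024 (+ 12 months), which agrees with the stated last visit. The current text postdates recruitment, so a change helps only children still under treatment or follow-up when it takes effect.

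**The case against.** The best defence is that the non-disclosure clause has an evident purpose. It stands beside the withdrawal from examinations and protects masked outcome assessment. The sentence giving the decision to the principal investigators most naturally concerns how long a child is followed or treated; it says nothing about allocation. No section makes management depend on the arm, and adverse effects are to be handled by standard procedures. The pages on investigators and facilities are not available for review, nor are the label example, the collaboration agreement or the investigator's brochure, so a practical contact route may exist there.

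Much of this stands as a limit on the claim. A reader might infer that nobody caring for a child could ever be told. The documents do not support that: the bar covers other study investigators, and neither an outside clinician nor the sponsor-investigator acting personally falls under it. A reader might also infer that a child would come to harm. The documents show different side-effect profiles by concentration, but they do not show that care would differ by arm.

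The core survives. A telephone number in an unseen page would not lift a written ban on sharing. The masking purpose does not require that ban to be absolute, because disclosure can be confined to one responsible person for one child. The result as written is also odd: an outside clinician may be told, while the responsible site investigator may not.

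**Conclusion.** The point holds in a limited form. The Randomization and Blinding sections, as written, give no route by which an emergency code break reaches a responsible study investigator other than the sponsor-investigator. This does not fit with Registration of adverse events and Criteria for aborting the study, and the four sections must be reconciled.

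The defect is in the wording of a safety procedure. It does not touch sample size, alpha or power. It is tempting to size it as all children at the sites where the sponsor-investigator does not work. The documents give neither that person's site nor the number of children per site, so no such count should be quoted. It would also be wrong to say that the existing withdrawal rule already confines the consequence to one child, since its wording is wider than that.

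The conclusion assumes that the removed or unseen pages contain no express exception to the non-disclosure sentence, and that the sections are meant to be followed literally.

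**What to change.** Reconcile Randomization, Blinding, Registration of adverse events and Criteria for aborting the study as follows:

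- Add an exception to the non-disclosure sentence: the result of an emergency code break may be given to the investigator or physician responsible for that child's care.
- Name a backup opener for when the sponsor-investigator is unavailable. Site-held envelopes, a right in the electronic case report form or a named deputy would each serve. The choice is the sponsor's, because each widens access to the codes to a different degree and the documents do not show what the electronic system can do.
- State that anyone unmasked is withdrawn from outcome measurements of that child and does not pass the allocation on to assessors. Clarify the present withdrawal sentence at the same time. Read literally, it could remove an unmasked site investigator from examining every participant.

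The cost is a protocol amendment of a few sentences plus whatever the chosen backup route needs. The downside is small: at each code break, one investigator is unmasked for one child and a masked colleague must take that child's measurements. Each site should confirm that it has such a colleague, since the documents do not describe staffing at that level.
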